4.13 Immunogenicity Assessments

Immunogenicity will be assessed by measuring serum nAb titers against wild-type SARS- CoV-2 virus (PRNT) and/or spike protein-expressing pseudovirus (microneutralization), serum binding antibody titers against spike protein and the spike protein receptor-binding domain (RBD) and peripheral blood mononuclear cell (PBMC) T cell responses against spike protein. Testing will include assessment of responses against spike protein of the original SARS-CoV-2 isolate as well as spike protein of variant Beta (B.1.315) and other variants. In Phase 1a, time points for evaluation will be at Study Days 1, 7, 28,

35, 56, 112, 224 and 336. In Phase 1b, time points for evaluation will be at Study Days 1, 7, 14, 28, 56, 84, 168 and 336. Neutralizing antibody and binding antibody results will be presented as the geometric mean titer (GMT) and the geometric mean fold increase in titer post-vaccination over baseline. T cell responses will be presented as the geometric mean number of IFN- γ ELISPOT-positive cells per 10^6 PBMCs.

A non-inferior GMT nAb titer against the GMT of the panel of COVID-19 convalescent sera (tested against the original Wuhan strain PNA for Phase 1a participants and against the B.1.351 beta variant PNA in Phase 1b) in subjects receiving 2 doses of VBI-2902a will justify proceeding with further clinical development; comparison of the nAb GMT against the WHO reference standard will be used to aid benchmarking against other COVID-19 vaccine candidates.

Similarly, the immunogenicity of VBI-2905a booster in previously vaccinated will be assessed in G4 participants by comparing it to G5 participants. A four-fold increase in the post-boost neutralizing antibody titer in the beta variant PNA will be considered as a confirmatory benchmark to advance clinical development of the 2905a vaccine candidate. If the results are not confirmatory, then the analysis of the RBD ELISA and IgG and T cell data will be undertaken by the SSC to make a decision to further the development of 2905a.

Immunogenicity results will be presented descriptively as point estimates and 95% confidence intervals (CIs), which will be tabulated by study group. Exploratory immunogenicity endpoints may include GMTs against variants of concern, as well as additional markers for T cell responses by ELISPOT and serum binding IgG subclasses as a marker of Th1 (IgG1 and IgG3) and Th2 (IgG4) dominated responses.

The immunogenicity population will include all participants who receive the prescribed study vaccine or placebo and underwent at least one immunogenicity assessment after vaccination.

The Study Steering Committee (SSC), comprised of representatives from the study sponsor (not involved in study operations) and external vaccine experts, will review unblinded immunogenicity data 7 days and 28 days after the first vaccinations (Phase 1a and Phase 1b)). The study will be unblinded following DSMB review of safety data collected through Day 56. Study participants will continue with study visits as planned up to 12 months of follow up after the first dose of study vaccine.

5 STUDY POPULATION

The study will enroll approximately 114 participants at study centers in Canada. Adherence to inclusion and exclusion criteria is essential to ensure safety to participants and precise comparison of control and treatment groups. Deviations from inclusion and exclusion criteria are not allowed because they could jeopardize the scientific integrity of the study, regulatory acceptability or participant safety.

Inclusion and exclusion criteria for specific parts of the study are defined below.

5.1 Inclusion and Exclusion Criteria

Inclusion Criteria

To be eligible for the study, each participant must satisfy ALL of the following criteria:

1. Healthy female and male participants 18-54 years of age
2. If female:
 - a. is of childbearing potential and must have a negative pregnancy test prior to study vaccinations and agree to use an effective method of birth control as deemed appropriate by the investigator (e.g., hormonal contraceptive, barrier contraceptive with additional spermicide, or an intrauterine device) beginning >30 days prior to the first study vaccine administration and continuing until the end of the study.

OR

- b. is not of childbearing potential, defined as postmenopausal (12 months with no menses without an alternative medical cause) or surgically sterile (bilateral tubal ligation, bilateral oophorectomy or hysterectomy).
3. Phase 1b: previously received a full course (2 doses) of an authorized S protein mRNA COVID-19 vaccine (e.g. COVID-19 vaccines produced by Pfizer/BioNTech or Moderna) at least 4 months prior to enrollment (1 month is defined as 28 days).
4. Sign an informed consent document indicating understanding of the purpose of and procedures required for the study and willingness to participate in the study.

Exclusion Criteria

Participants with any of the following criteria will be excluded:

1. History of clinical or laboratory diagnosis of COVID-19 or SARS-CoV-2 infection
2. **Phase 1b:** Previous receipt of an experimental or authorized SARS-CoV-2 (COVID-19) vaccine other than an S protein mRNA vaccine.
3. **Phase 1a:** Previous receipt of an experimental or authorized SARS-CoV-2 (COVID-19) vaccine.
4. Positive PCR or rapid antigen test for SARS-CoV-2 at screening.
5. Individuals with chronic medical conditions, including any of the following:
 - a. Diabetes mellitus Type 1 or Type 2
 - b. Chronic pulmonary disease (e.g., COPD or Asthma)
 - c. Hypertension (e.g., SBP >140 mmHg or DBP >90 mmHg)
 - d. Chronic kidney disease (e.g., GFR <60 mL/min/1.73 m²)
 - e. Chronic liver disease
 - f. Obesity (e.g., BMI >30 kg/m²)
6. Any history of cancer requiring chemotherapy or radiation within 5 years.

7. Other medical or psychiatric condition including recent (within the past year) or active suicidal ideation/behavior or laboratory abnormality that may increase the risk of study participation or, in the investigator's judgment, make the participant inappropriate for the study.
8. The lack of participant's capacity (mental, social, behavioral), in the investigator's judgement, to provide informed consent for participation in the study
9. Known or suspected impairment of immunological function, including but not limited to autoimmune diseases:
 - a. autoimmune diseases (e.g. multiple sclerosis, type 1 diabetes, myasthenia gravis, Crohn disease and other inflammatory bowel diseases, celiac disease, systemic lupus erythematosus, scleroderma, including diffuse systemic form and CREST syndrome, systemic sclerosis, dermatomyositis/polymyositis, rheumatoid arthritis, juvenile idiopathic arthritis, autoimmune thyroiditis -including Hashimoto thyroiditis, Grave's or Basedow's disease, immune thrombocytopenic purpura, autoimmune hemolytic anemia, autoimmune hepatitis, psoriasis, vitiligo, vasculitis, Guillain-Barré syndrome, Transverse myelitis, Addison's disease, Bell's Palsy and Alopecia Areata);
 - b. secondary immunodeficiency disorders (e.g., Acquired Immunodeficiency Syndrome caused by Human Immunodeficiency Virus infection (HIV/AIDS), solid organ transplant, splenectomy);
 - c. primary immunodeficiency disorders (e.g., common variable immune deficiency (CVID), Defective phagocytic cell function and neutropenia syndromes, complement deficiency).
10. History of allergic reactions or anaphylactic reaction to any vaccine component.
11. Known infection with human immunodeficiency virus (HIV), hepatitis C virus (HCV), or hepatitis B virus (HBV).
12. Pregnant or breastfeeding or plans to conceive from 2 weeks before the study until the end of study.
13. Clinically significant abnormal physical examination, vital signs, or clinically significant abnormal values for hematology, serum chemistry or urinalysis at screening as determined by the investigator.
14. Any laboratory test abnormality that would be considered of Grade 1 severity or above (as per FDA grading guidelines) and is considered as clinically significant by the investigator. Grade 2 severity or above is exclusionary, regardless of clinical assessment.
15. Has received blood products or immunoglobulin within 90 days of enrollment or is likely to require blood products during the study period.
16. Chronic administration (defined as more than 14 days in total) of immune-suppressive or

other immune-modifying drug within six months prior to the product dose (for corticosteroids, this is defined as prednisone ≥ 20 mg/day or equivalent). Inhaled and topical steroids are allowed.

17. Immunization with attenuated vaccines (e.g., MMR) within 4 weeks prior to enrollment.
18. Immunization with inactivated vaccines (e.g., influenza) within 2 weeks prior to enrollment.
19. Participation in another clinical study within 30 days.
20. Any skin abnormality or tattoo that would limit post-vaccination injection site assessment.
21. Family members of study site personnel.

5.2 Protection of Participants

Informed Consent:

Each local research ethics board (REB) or research ethics committee (REC) will review and approve the study protocol, informed consent form and other study-related documentation.

Written informed consent will be obtained after participants have read the approved informed consent form and have had adequate opportunity to discuss the study with an investigator or a qualified designee and before the initiation of any study related procedures.

Data Safety Monitoring Board (DSMB):

While the trial is ongoing, to allow regular review of the accumulated safety data, a DSMB will be established to perform early review of blinded post-vaccination safety data at 7 and 28 days after each vaccination (solicited and unsolicited AEs and safety labs) and regularly thereafter through study termination. Second vaccinations will only be administered after the DSMB confirmation that safety after the first dose is acceptable and that stopping rules have not been met. The DSMB may recommend to continue, pause, modify, or suspend the further enrollment to the study. Stopping rules can be found in [Section 10.7](#).

5.3 Follow-up Duration

Participants will be followed a minimum of 12 months (assuming 28 days per month) after the Day 1 immunization with at least six months follow-up safety assessments after final dose or early withdrawal (EW) (see [Section 8](#)).

6 STUDY PROCEDURES AND INTERVENTIONS

An overall table of study treatments is provided in [Table 3](#) below. The schedule of events is located in [Section 4, Table 1, and Table 2](#) above.

Table 3: Overall Summary of Study Treatments

Part	Group	Treatment name	Dose (µg)	Alum	Participant age (years)	Total participants
Phase 1a	G1	VBI-2902a	5	Yes	18-54	20
	G2	VBI-2902a	5	Yes	18-54	20
	G3	Placebo	None	No	18-54	20
Phase 1b	G4	VBI-2905a	5	Yes	18-54	27
	G5	Placebo	None	No	18-54	27
	Total					114

6.1 Detailed Description of Study Procedures

Informed consent:

The signed informed consent must be obtained before study participation.

6.1.1 Check inclusion and exclusion criteria:

Verification of ongoing eligibility to be completed by the investigator or qualified designee prior to vaccine administration.

6.1.2 Collect demographic data:

Record demographic data such as date of birth, gender, height, weight, and ethnicity in the participant's eCRF.

6.1.3 Medical history:

Obtain the participant's medical history by interview and/or review of the participant's medical records and record any pre-existing conditions or signs and/or symptoms present in a participant prior to the first study injection in the eCRF. Information collected will include participant's COVID-19 vaccination status, including date of last vaccination and type of vaccine, if vaccinated.

6.1.4 Physical examination:

Perform a full physical examination at the screening visit or at Day 1 prior to injection; history-directed physical examination can be completed at subsequent visits. Full physical examination should include vital signs: weight, height, blood pressure, pulse rate and respiratory rate.

If the investigator determines that the participant's health on the day of injection temporarily precludes injection, the visit will be rescheduled. Collected information needs to be recorded in the eCRF.

Treatment of any abnormality observed during this examination has to be performed according to local medical practice outside this study or by referral to an appropriate health care provider.

6.1.5 Vital Signs:

Vital signs (body temperature, blood pressure, heart rate, respiration rate) will be measured pre-vaccination and 60 minutes (+10 minutes window) post-vaccination.

6.1.6 Check contraindications, warnings and precautions to injection:

Contraindications, warnings and precautions to injection must be checked at the beginning of each injection visit on Days 1 and 28.

6.1.7 Pregnancy test:

Urine pregnancy tests must be confirmed negative at screening and prior to study vaccine administration.

6.1.8 Assess pre-injection body temperature:

The body temperature of all participants needs to be measured using the study supplied thermometer prior to any study product administration. The preferred route for this study is oral and the participant should be instructed to refrain from eating or drinking 60 minutes prior to obtaining the temperature. If the participant has a fever (defined as temperature $\geq 38.0^{\circ}\text{C}/100.4^{\circ}\text{F}$ oral) on the day of injection, the injection visit will be rescheduled within the allowed interval for this visit.

6.1.9 Telemedicine or home visits:

Due to the ongoing COVID-19 outbreak, growing emergency measures are being put in place to limit the spread of the outbreak, including government and institutional restrictions. These restrictions may affect how the study is conducted during this time. Possible changes, which could impact study visits include, for example, use of available technology for remote monitoring/data collection, “virtual” study visits, electronic completion/transmission of study- related questionnaires, and/or any other changes (telephone, email or text message contact, alternative location for assessment, including local laboratories or home visits) deemed necessary until the pandemic and associated government/institutional restrictions are lifted. Some blood samples may be drawn using local lab services, and the sponsor may arrange home visits if site visits cannot occur.

6.1.10 Study group and treatment number allocation:

Participants in Phase 1a and Phase 1b will be randomized using a stratified permuted block randomization. In Phase 1a, participants aged 18 – 54 will be randomized 2:1 to receive VBI-2902a or placebo. In Phase 1b subjects aged 18-54 will be randomized 1:1 to receive VBI-2905a or placebo.

For the Phase 1b part of the study, the sites will only enroll participants who have previously received mRNA COVID-19 vaccines.

Figure 1 describes the enrollment and safety evaluation by regimen, age group, and dose-level.

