- One additional exclusion criterion was added - the lack of participant's capacity (mental, social, behavioral) to provide informed consent
- Section 4.13, Immunogenicity Assessments, was modified to clarify how neutralizing antibody results will be assessed
- Section 6.1.7, Biological Sample Handling and Analysis, was modified to indicate that Nexelis will perform sequencing of SARS-CoV-2 in nasal/nasopharyngeal swab samples
- Pseudoneutralization assay (PNA) was added to the list of abbreviations

Version 4.1 (20 July 2021)

Rationale: A minor protocol amendment was made with the following changes:

- Replace references to Phase 1 and Phase 2 parts of the study with Phase 1a/1b throughout the Protocol. Due to study design changes made in the Protocol Amendment v4.0, designation of the study as a Phase 1a/1b more accurately reflects the early nature of this study
- Clarify that humoral and cell-mediated immunogenicity will be tested in all study participants (Tables 1, 2, and 3 and throughout the document)
- Deleted a duplicate line for assessment of concomitant medications (Tables 1, 2, and 3)

Version 4.0 (28 June 2021)

Rationale: A major protocol amendment was made to include unblinding of study groups after Day 56 in Phase 1 and Phase 2 and to revise the Phase 2 study design with the following changes:

- Modify eVLP to express S protein of South African variant B.1.351 (VBI-2905a) in place of S protein of Wuhan isolate (VBI-2902a)
- Modify the eVLP formulation for VBI-2905a to provide greater vaccine stability
- Change the number of study participants, modify eligibility criteria to include healthy adults age ≥ 18 years with or without a history of prior COVID-19 vaccination, (mRNA vaccine only) and stratify randomization of the study based on the previous COVID-19 (mRNA) vaccination status
- Modify immunological assay sampling schedule for alignment with clinical trials of other vaccine candidates and to reduce the number blood draws for cell-mediated immunity assays
- Add immunological analysis of responses against SARS-CoV-2 variants
- Collect duplicate nasopharyngeal swabs at study visits and store one swab frozen for potential sequencing of viral RNA
- Change references to Health Canada to read “appropriate regulatory authorities” to reflect the addition of clinical sites in Mexico

These changes required extensive revisions throughout the protocol.

Version 3.1 (04 February 2021)

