10.4 Randomization

Treatment allocation for Phase 1a and Phase 1b will be done through an interactive response technology (IRT) system (interactive web response system, IWRS). Access to the IWRS will be through individual login and password. To enroll a new subject, the authorized staff at the site will be prompted to complete a randomization page including the subject's age, and other demographic information and to confirm individually the presence of all inclusion criteria, and the absence of all exclusion criteria. Upon confirmation that all inclusion criteria and no exclusion criteria are met the subject will be randomized. Blinded confirmation of the randomization will be sent by E-mail to the site and should be retained in the study files. The site pharmacy and/or unblinded study center staff will receive a notification for a unique subject randomization assignment, which must be filed in a locked area/computer folder not accessible by blinded study center staff. Specific instructions for use of the IWRS will be provided separately.

Randomization numbers will NOT be reused for any reason.

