10.6.2 Safety Analysis

The safety analysis will be performed on all participants receiving at least one dose of the study vaccine/placebo (the safety population). Safety will be evaluated using the participants' recorded safety observations (Diary Cards), reports of AEs, SAEs, or pregnancy, reports of significant health events, physical examination findings, clinical laboratory results, vital signs, and concomitant medication use.

The local and general AEs/SAEs will be evaluated using FDA Guidance for industry: Toxicity grading scale for healthy adult and adolescent volunteers enrolled in preventive vaccine clinical studies and causality assessment scale (see [Sections 8.5](#) and [8.6](#)).

The verbatim terms used in the eCRFs by investigators to identify AEs will be coded using the Medical Dictionary for Regulatory Activities (MedDRA). All eCRF-reported AEs with onset post-immunization will be included in the analysis. For each AE, the percentage of participants who experienced at least one occurrence of the given event will be summarized by treatment group and age stratum.

Special attention will be given to those participants who died, who discontinued study due to an AE, or who experienced a severe or a serious adverse event (e.g., summaries, listings, and narrative preparation may be provided, as appropriate) or experience an allergic or allergic-like reaction.

An aggregate event "Any" will be defined as the maximal severity of the combined events "Local" and "General".

Fisher's Exact Test will be used to assess differences in rates of solicited adverse events between treatment groups. All statistical tests performed will be 2-sided with Type I error of 5%. No adjustments will be made for multiplicity of tests performed.

In addition, all safety data will be analyzed descriptively. All of the information captured on the participants' Diary Cards will be presented by participant in the data listings.

Descriptive statistics for selected laboratory parameters will be presented by treatment group.

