3.2 Randomization and Study Treatments

Randomization of subjects will vary based on which phase and part of the study is currently enrolling. Description of the randomization allocations & treatment arms is outlined in the description of the study design above.

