6.4.2 Analysis of Immunogenicity Endpoints

The immunogenicity endpoints are defined in Section 2.

- GMT and the geometric mean fold increase (GMFR) in serum antibody titer post-vaccination over Day 1 (baseline) at Days 7, 28, 35, 56, 112, 224 and 336 (Phase 1a, groups G1, G2 and G3); at Days 7, 14, 28, 56, 84, 168 and 336 (Phase 1b groups G4 and G5);
 - Neutralizing activity against multiple variant spike protein-expressing pseudovirus, and/or PRNT₉₀ neutralizing activity against wild-type SARS-CoV-2 virus and the variant Beta (B1.351) in all participants.
 - RBD Antibody titers against wild-type variant spike protein measured by ELISA.

Confidence intervals for the difference of geometric means will be included for the pairwise comparison of treatment groups.

The 95% CI for GMTs will be obtained within each group separately. The 95% CI for the mean of log-transformed titer/concentration will be first obtained assuming that log-transformed concentrations/titers are normally distributed with an unknown variance. The 95% CI for GMTs will be then obtained by exponential-transformation of the 95% CI for the mean of log-transformed titers using analysis of variance (ANOVA) model.

SAS® Code for comparing GMTs:

```
PROC MIXED DATA=<Data>; * specify and sub-select data set as applicable;
```

```
*BY Agegrp; * as applicable;
```

```
CLASS trtpn; * other factors may be added, if applicable;
```

```
MODEL AVAL = trtpn; * AVAL=10**titer
```

```
* add factors and options (e.g. ALPHA=.. Solutions) as applicable;
```

```
LSMEANS trtpn / CL ALPHA=0.05 STDERR; * modify/adapt as applicable
```

```
Ods output LSMEANS =_outmix;
```

```
RUN;
```

```
QUIT;
```

```
Data _outmix;
```

```
Set _outmix;
```

GMT= 10**(Estimate);

GMT_LCL = 10**(Lower);

GMT_UCL = 10**(Upper);

RUN;

The GMFR will be derived by using Analysis of Covariance (ANCOVA) to model the difference in the log of the titer values between post vaccination (Day 56) and baseline (Day 0), with treatment group as main effect and baseline titer as covariate. The GMFR will be compared between the treatment groups. Pair-wise comparisons between the treatments groups will be performed using two-sided, 95% confidence, based on the least-squares mean differences from the ANCOVA model.

SAS® Code for comparing GMFR:

```
PROC MIXED DATA=<Data> (analysis dataset);  
class trtpn;  
model diff= trtpn Base; * diff = log10Day56 – log10Day0. Base=log10Day0  
Lsmeans trtpn/cl alpha=0.05;  

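### Both phases are said to use stratified randomization, but no factor is named and neither immunogenicity model includes one; if the factor predicts titer, the between-group intervals are conservative and precision is forgone

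*Protocol*

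**What the plan says.** Protocol 6.1.10 gives the allocation method: "Participants in Phase 1a and Phase 1b will be randomized using a stratified permuted block randomization". It names no factor, number of strata or block size. Protocol 10.4 says that site staff will "complete a randomization page including the subject's age, and other demographic information", but calls none of these entries a stratification factor. SAP 3.2 says "Randomization of subjects will vary based on which phase and part of the study is currently enrolling" and then "Description of the randomization allocations & treatment arms is outlined in the description of the study design above"; the design section it points to gives allocation ratios only.

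In SAP 6.4.2 the GMT code carries the line "CLASS trtpn; * other factors may be added, if applicable", and its model statement has treatment as the only term. The GMFR code is "model diff= trtpn Base", with no provision for further factors. The same section plans pairwise comparisons of GMT and of GMFR between treatment groups.

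Two remnants bear on what the strata might be:

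- Protocol 10.6.2 says that adverse events "will be summarized by treatment group and age stratum". SAP 6.3.1.2 also plans displays by age group, and the GMT code has a commented-out BY statement for age group.
- The amendment history for Version 4.0, which describes superseded text, records a decision to "stratify randomization of the study based on the previous COVID-19 (mRNA) vaccination status".

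**The concern.** Stratified blocks balance the arms on the stratification factor, which reduces the true sampling variance of the treatment difference. A model that omits the factor leaves the between-stratum variance in its residual. If the factor predicts titer, the reported standard error is then larger than the true one: the interval over-covers, and the precision that stratification was meant to buy is not used.

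The contrasts affected matter to the sponsor. Protocol 4.13 assesses the VBI-2905a booster by comparing G4 with G5, and Protocol 10.2 and SAP 3.3 claim 80% power for a two-fold difference in neutralizing titer. Groups of 20 to 27 leave little precision to spare. The open comment in the GMT code also leaves the model to be settled later, in a trial where each phase is unblinded after the Day 56 safety review (Protocol 8.7.1, SAP section 7).

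**Working it through.** **1. What the strata could be.** The current text leaves few candidates.

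- *Prior mRNA vaccination* is constant within each phase. Phase 1a excludes anyone previously vaccinated against COVID-19, and Phase 1b enrolls only mRNA recipients.
- *Age* is a single band, 18-54, with no cut-point (Protocol 5.1).
- *Site or another demographic variable* is possible, but no passage says so.

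Whether any phase has two or more strata therefore cannot be settled from the documents.

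**2. The plan's own figure.** A two-fold difference is log10(2) = 0.301. Two-sided alpha of 0.05 and 80% power give z = 1.960 + 0.842 = 2.802. No SD is stated, and Protocol 10.3 says no formal power calculation is reported, so the 80% cannot be reproduced. The SD it implies is 0.301 / (2.802 × √(2/n)):

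- n = 20 per group: 0.301 / (2.802 × 0.316) = 0.340 (t-based 0.331)
- n = 24 per group (48 completers in Phase 1b): 0.301 / (2.802 × 0.289) = 0.372 (t-based 0.364)

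**3. Effect of leaving the factor out.** Let R² be the share of log-titer variance explained by the strata. The documents do not give it, so a range is shown. With balanced allocation:

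- unadjusted / adjusted interval width (log scale) = 1/√(1−R²)
- adjusted power = Φ(2.802/√(1−R²) − 1.960)
- unadjusted power = Φ(0.842/√(1−R²))
- unadjusted type I error = 2 × [1 − Φ(1.960/√(1−R²))]

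Example at R² = 0.20: 1/√0.80 = 1.118. Adjusted power is Φ(3.133 − 1.960) = 87.9%, and unadjusted power is Φ(0.941) = 82.7%.

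| R² | Width ratio | Unadjusted power | Adjusted power | Unadjusted type I error |
|---|---|---|---|---|
| 0 | 1.000 | 80.0% | 80.0% | 0.050 |
| 0.05 | 1.026 | 80.6% | 82.0% | 0.044 |
| 0.10 | 1.054 | 81.3% | 84.0% | 0.039 |
| 0.20 | 1.118 | 82.7% | 87.9% | 0.028 |
| 0.30 | 1.195 | 84.3% | 91.8% | 0.019 |

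The table starts from the stated 80%. A simulation at 20 per group (two balanced strata, SD 0.331, 20,000 replicates) agrees: at R² = 0.20, power was 82.0% unadjusted and 87.9% adjusted.

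**4. A Phase 1b scenario.** Assumptions: 24 completers per arm, four equal strata, blocks of 4, total SD 0.4 log10, 4,000 simulated trials per row.

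| R² | Width ratio | Unadjusted coverage | Unadjusted power | Adjusted power |
|---|---|---|---|---|
| 0 | 1.00 | 95.3% | 71% | 71% |
| 0.10 | 1.06 | 96.0% | 73% | 77% |
| 0.20 | 1.12 | 97.3% | 75% | 81% |
| 0.30 | 1.20 | 98.1% | 75% | 86% |

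Repeat runs moved no power figure by more than one percentage point. Down the column, unadjusted power rises slightly; the gap to the adjusted column is the gain not taken (4, 6 and 11 points).

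**5. Scope.** These results concern between-group differences in log titer. They do not apply to the single-group GMT intervals, which SAP 6.4.2 obtains within each group. They were not computed for the GMFR model, whose baseline covariate may already absorb part of a stratum effect.

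**The case against.** The strongest reply is that *stratified* may be leftover wording. The one factor ever named belongs to superseded text and is now constant within each phase, and age is one band. Other remnants survive nearby: Protocol 6.1.10 says Figure 1 describes enrollment by age group and dose level, and SAP 6.4.1 still refers to a 10 µg dose group and age cohorts. Protocol 10.4 says IWRS instructions are provided separately, so the factor list may sit in a document not seen here. With one stratum per phase, the models omit nothing. This stands, and it is why the statistical consequence can only be stated conditionally.

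It is also fair that the variance shares are assumptions. Each antibody assay is assigned to one laboratory (Protocol 6.1.17) and the participants are a narrow healthy group, so a site effect could be small. Protocol 10.3 calls the immunogenicity results exploratory, and the convalescent-serum benchmark is not a randomized comparison, so balance between arms does not bear on it.

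The comment allowing other factors in the GMT code is a weaker defense. It fixes no factor, and the GMFR code has no equivalent.

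A reader might go further and infer that the intervals *are* too wide and that the two-fold comparison *loses* power. The documents support neither. The first needs at least two strata and a prognostic factor, and neither is documented. The second is contradicted by the arithmetic: unadjusted power does not fall below its no-strata value, and type I error stays at or below about 5%.

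**Conclusion.** The gap in specification is established without assumptions: the protocol declares stratified allocation for both phases, no current text names a factor, and neither prespecified model includes one. The age-stratum displays cannot be programmed as written, because no age cut-point exists.

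The statistical cost is conditional. With at least two strata and a factor explaining 10, 20 or 30% of log-titer variance, between-group intervals are about 5-6, 12 or 20% wider than adjusted ones on the log scale. In Phase 1b at an assumed SD of 0.4, power is about 73, 75 or 75% instead of 77, 81 or 86%. The cost is zero with one stratum or a non-prognostic factor, and probably smaller for GMFR. The error is conservative and does not threaten validity. The point is worth correcting because the better analysis costs almost nothing and should be fixed in advance.

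**What to change.** Take the stratification factor(s) and levels actually used from the IWRS specification. Name them in Protocol 6.1.10 and 10.4 and in SAP 3.2. Before unblinding, prespecify them as CLASS fixed effects in both PROC MIXED models:

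- GMT: log10 titer = trtpn + stratum
- GMFR: diff = trtpn + stratum + Base

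Replace the open comment about other factors with this list, and set a rule in advance for pooling sparse levels. For any phase already unblinded, say in SAP section 7 that the term was added afterwards, and show the model without it alongside.

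If the specification shows one stratum per phase, leave the models as they are. Delete *stratified* from Protocol 6.1.10, and remove the age-stratum and age-group displays from Protocol 10.6.2 and SAP 6.3.1.2 and the BY option from the GMT code.

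The cost is a few lines of text, one term per model and a few degrees of freedom. With 48 completers in two arms and an assumed four strata, residual degrees of freedom in the GMT model go from 46 to 43. In the simulation this had no visible cost in power when the strata explained nothing (71% either way).
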